5. STUDY DESIGN AND CONDUCT CONSIDERATIONS

5.1 Study Design

This study is a multi-center, prospective, non-blinded, one to one randomized study. A total of 160 adult patients, 80 in each study arm, will be enrolled at up to 15 investigational sites in the United States (US) and Canada. Patients meeting all of the inclusion criteria and none of the exclusion criteria of this protocol, and deemed treatable by either CRRT with Prismocitrate 18 solution or CRRT with no systemic anticoagulation, are eligible for enrollment in the study. If a patient is already receiving standard-of-care CRRT, they must be randomized within 24 hours of initiation of their standard-of-care CRRT. All patients will be treated with predilution CVVHDF as the study CRRT modality. Patients enrolled in the study will receive either Prismocitrate 18 anticoagulation or no systemic anticoagulation during their study CRRT, and extracorporeal circuit life will be monitored for up to 120 hours of study CRRT (treatment period). During the treatment period, the adequacy of anticoagulation in the Prismocitrate 18 patients will be assessed by monitoring extracorporeal circuit pressures and by assessment of systemic and post-filter blood iCa concentrations. Patients will be monitored for acid-base parameters and serum electrolytes at baseline prior to any CRRT), initiation (after randomization but before the initiation of study CRRT) and at pre-determined intervals during treatment. Information on bleeding events (number, location, duration) and the number and type of blood transfusions along with the number of units infused will also be collected.

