8.1 General/Types of Analyses

Unless otherwise specified, treatment effects will be evaluated on the basis of a 2-sided significance level of 0.050 (when rounded to 3 decimal places). All analyses will be performed using Statistical Analysis Software (SAS®), SAS/GRAPH® and SAS/STAT® software, Version 9.2 of SAS for Windows, Copyright© 2018 SAS Institute Inc., on a Microsoft Windows Server. SAS and all other SAS Institute Inc. product or service names are registered trademarks or trademarks of SAS Institute Inc., Cary, NC, USA¹0.

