13.3 Secondary Analysis

A descriptive summary of systemic and post-filter blood iCa²⁺ concentrations as assessed at baseline (systemic only), 1 hour and every 6 hours during the 120 hours evaluation period and at 120 hours or end of the Evaluation period will be provided by treatment group. This summary will use the number of subjects n, mean, standard deviation, minimum, median and maximum. Changes from baseline will be analyzed by the number of subjects n, mean and standard deviation and t-test or Wilcoxon rank sum test, as applicable.

The individual blood iCa²⁺ concentrations will further be displayed graphically over time for each of the two treatment groups.

A MMRM analysis will be deployed to evaluate differences between treatment groups in blood i Ca^{2+} concentrations that are collected at baseline, 1 hour and every 6 hours during the 120 hours Evaluation period and at 120 hours or end of the Evaluation period from the initiation of CRRT. The model will include the illness severity score APACHE II, baseline i Ca^{2+} concentration, treatment group and time point as fixed effects, and an interaction between time point and treatment group will be included in the model only if treatment effects differ statistically significantly over time (p < 0.01).

In addition, frequencies and percentages will be provided for $iCa^{2+} < 1.1 \text{ mmol/L}$ by time point and treatment group (threshold indicative of decrease in iCa^{2+} despite adequate calcium compensation).

Daily delivered dose and overall delivered dose (both in mL/kg/hour) will be summarized using the number of subjects n, mean, standard deviation, minimum, median and maximum, as applicable. Treatment exposure will be analyzed carrying out the same descriptive summary for the percentages of the prescribed dose actually administered to the patient.

Effluent rate is considered an appropriate surrogate for the CRRT dose. Therefore, prescribed and delivered CRRT dose will be derived as follows based on the University of Alabama at Birmingham Continuous Venovenous Hemodiafiltration Protocol¹² used in the study:

$$Q_E = Q_{PBP} + Q_D + Q_{FR} + Q_R$$

where Q_E is the effluent rate (mL/hour),

Q_{PBP} is the pre-blood pump infusion rate which is the Prismocitrate 18 flow rate (mL/hour),

Q_D is the dialysate flow rate (mL/hour),

Q_{FR} is the patient fluid removal rate (mL/hour), and

Q_R is the post-filter replacement fluid rate (mL/hour).

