14.3 Serum Bicarbonate, pH, Blood Total Calcium and Serum Electrolytes

Serum bicarbonate, pH (ABG), blood total calcium concentrations and serum electrolytes (sodium, potassium, chloride, phosphate, magnesium) will be analyzed in the exact same manner as blood iCa²⁺ concentrations.

Along the lines of Section 13.3 Secondary Analysis descriptive summaries will be carried out for each parameter at the different assessment time points, and changes from baseline will be analyzed. A MMRM analysis will be deployed for the different parameters following the description under Section 13.3.

The total calcium/iCa²⁺ ratio will only be summarized descriptively. Frequencies and percentages will be provided for pH < 7.2 by time point and treatment group (threshold indicative of metabolic acidosis). Frequencies and percentages will further be provided for total calcium/iCa ratio > 2.1 by time point and treatment group (threshold suggestive of citrate accumulation) as well as for anion gap > 11 mmol/L (threshold indicative of metabolic disturbance) and base excess < -5 mmol/L.

Complete blood count and blood lactate measurements obtained at screening will be listed by patient.

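### The MMRM for ionised calcium and the safety laboratory values keeps treatment-by-time only if its own test gives p < 0.01, so the modelled effect can dilute a gradual, moderate late difference

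*SAP*

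**What the plan says.** SAP 13.3 specifies an MMRM for blood iCa with APACHE II, baseline iCa, treatment and time point as fixed effects. On the interaction it says that "an interaction between time point and treatment group will be included in the model only if treatment effects differ statistically significantly over time", at p < 0.01. Measurements are taken at "1 hour and every 6 hours during the 120 hours evaluation period". SAP 14.3 states that bicarbonate, pH, total calcium and electrolytes "will be analyzed in the exact same manner as blood" iCa, and that "A MMRM analysis will be deployed for the different parameters following the description under Section 13.3". The table list in SAP section 18 also shows MMRM output for base excess and anion gap, making 11 modelled parameters.

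The total calcium/iCa ratio is treated differently. SAP 14.3 says that this "ratio will only be summarized descriptively", with counts above 2.1 at each time point.

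The SAP does not name a covariance structure and does not say whether time is categorical. SAP 8.5 brings additional, unscheduled draws into the MMRM. Protocol 8.5.2 and 8.6 call for MMRM analyses without listing model terms.

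**The concern.** The form of the model is chosen by a pre-test on the trial data. If the interaction is left out, the model assumes the same treatment difference at every hour and estimates one average. Patients leave over time, so that average leans towards the early hours.

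This matters because several of these parameters are followed to detect drift over days. Protocol 2.2 and 5.2.3 name anion gap, base excess, pH and falling iCa, alongside the calcium ratio, as signs of citrate accumulation. Each of these four has an MMRM. For a difference that appears only on days 3 to 5, the constant-effect model answers a question nobody asked, and a broad test at a strict threshold may not reveal it.

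**Working it through.** The plan gives no power figure for the MMRM or its interaction test, so there is none to reproduce.

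**From the documents**
- 80 per arm: "A total of 160 adult patients, 80 in each study arm".
- Post-start times (SAP Table 2): iCa and total calcium at 1 h and then 6, 12, …, 120 h, which is 21. Bicarbonate, pH, base excess, electrolytes and anion gap have no 1 h draw, which leaves 20.
- Interaction df with categorical time: 21 − 1 = 20, or 20 − 1 = 19.
- Pre-test level 0.01. General level: "2-sided significance level of 0.050 (when rounded to 3 decimal places").

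**Assumed (not in the documents)**
- Difference d(t) = 0 up to 48 h, then 0.6 × (t − 48)/72, in units of the SD at one time point after covariate adjustment.
- Share g of patients gone by 120 h: 0.5 or 0.7, equal in both arms, with retention S(t) = (1 − g)^(t/120).
- Correlation between two times: b + (1 − b) r^(gap/6 h), with b = 0.2 or 0.5 and r = 0.5 or 0.8.

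**Simple dilution.** The ramp fractions at 54, 60, …, 120 h are 1/12, 2/12, …, 12/12, which sum to 6.5. Over 21 times the unweighted mean is 6.5/21 = 0.31, so 0.31 × 0.6 = 0.19 SD before dropout shifts the weight earlier.

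**Generalised least squares with known covariance**
- Information per arm: 80 × Σ p_j R_j⁻¹. Here p_j = S(t_j) − S(t_j+1) is the share whose last value is at time j (at 120 h, p = S(120)), and R_j is the correlation matrix up to that time, padded with zeros.
- V = 2 × (information)⁻¹ is the variance of the vector of time-specific differences d.
- Constant-effect estimate: 1′V⁻¹d / 1′V⁻¹1, with standard error (1′V⁻¹1)^(−1/2).
- Interaction test: λ = (Cd)′(CVC′)⁻¹(Cd), where C takes differences from the first time. Power is P(χ²₂₀(λ) > 37.57).
- 120 h contrast: Φ(0.6/SE₁₂₀ − 1.96).

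Results with 21 times:

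| b | r | gone by 120 h | interaction kept | average (SD) | power, average | power, 120 h contrast |
|---|---|---|---|---|---|---|
| 0.2 | 0.5 | 50% | 24% | 0.14 | 30% | 79% |
| 0.2 | 0.5 | 70% | 13% | 0.10 | 18% | 59% |
| 0.2 | 0.8 | 50% | 13% | 0.15 | 26% | 81% |
| 0.2 | 0.8 | 70% | 8% | 0.11 | 16% | 62% |
| 0.5 | 0.5 | 50% | 48% | 0.13 | 18% | 85% |
| 0.5 | 0.5 | 70% | 25% | 0.09 | 11% | 70% |
| 0.5 | 0.8 | 50% | 26% | 0.14 | 19% | 86% |
| 0.5 | 0.8 | 70% | 14% | 0.10 | 12% | 71% |

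The average is 0.09/0.6 = 15% to 0.15/0.6 = 25% of the 120 h difference.

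**Other assumptions change the frequency.** For a 0.5 SD difference at 120 h, retention of 30–100%, and an F(20, 158) reference distribution, the interaction is kept as follows:
- Ramp from 72 h: 3–20% under serial correlation, but 31–96% under compound symmetry (correlation 0.5).
- Step at 96 h: 14–98% under AR(1), and 68–100% under compound symmetry.
- Linear from 0 h: 3–10% under serial correlation, and 35–90% under compound symmetry.

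For a ramp from 72 h to 1.0 SD it is 25–96% under serial correlation and 100% under compound symmetry.

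**The case against.** Four stronger readings are tempting, and the documents do not support them.

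*That the interaction would usually be lost.* This depends on effect shape, effect size, covariance and dropout, none of which the documents give. The ranges above run from 3% to 100%. The assumed dropout also implies 1 − 0.5^0.6 = 34% to 1 − 0.3^0.6 = 51% gone by 72 h, although inclusion criterion 5 requires patients expected to stay on CRRT that long. And if time were entered as a continuous variable, the interaction would have 1 df and the low-power argument would fall away. The SAP does not say which is meant.

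*That citrate accumulation would be hidden.* Its lead marker, the total calcium/iCa ratio, is in no MMRM and is tabulated by time point. Accumulation in individual patients is in any case better seen in threshold counts than in a mean difference. What stands is that anion gap, base excess, pH and iCa, the other named signs, are modelled.

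*That a late shift would reach the report only as one non-significant number.* SAP 13.3 and 14.3 also plan summaries by time point, plots of individual iCa values over time, counts for iCa < 1.1, pH < 7.2, anion gap > 11 and base excess < −5, and t-tests or Wilcoxon tests of change from baseline. If those tests are run at each time, which is the natural reading, a plain t-test at 120 h in the same scenario has about 53% power (80 × 0.3 = 24 left per arm) to 75% (80 × 0.5 = 40 left). The gain from the full model (59–86%) is real but modest.

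*That the SAP contradicts the protocol.* The protocol lists no MMRM terms, and its section 8.1 leaves detail to the SAP. Silence is not a conflict.

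It is also fair to say that the rule is prespecified and that these analyses carry no confirmatory claim. This limits the consequences, but the constant-effect estimate is still a poor summary of a late effect.

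**Conclusion.** The concern holds as a weakness of the modelled estimates for iCa, bicarbonate, pH, total calcium and electrolytes and, by the table list, anion gap and base excess. With time as categories, the p < 0.01 rule can drop the interaction when a gradual, moderate late effect is real. In the assumed scenario it is kept in about 8–48% of trials. Otherwise a 0.6 SD difference at 120 h is reported by the model as about 0.09–0.15 SD, with 11–30% power, against 59–86% for the 120 h contrast from a model that keeps the interaction. These figures rest on the stated effect shape, serial correlation and 50–70% loss by 120 h. They illustrate the mechanism and do not predict this trial.

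The total calcium/iCa ratio, the by-time summaries, the threshold counts, the change-from-baseline tests and the primary endpoint are not affected. The change is worth making, but nothing confirmatory depends on it.

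**What to change.** In SAP 13.3, and through it 14.3:
- Delete the p < 0.01 rule and always include treatment by scheduled time point, with time categorical. Assign additional draws to the nearest scheduled time, and state which value counts when two fall in the same slot.
- Report the difference and confidence interval at each time point, plus the time-averaged difference as a prespecified contrast from the same model.
- Label these results descriptive, with no multiplicity adjustment.

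Relaxing the pre-test to 0.05 would not be enough. For the 0.5 SD ramp from 72 h under serial correlation, the interaction would still be kept in only 13–42% of trials.

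The cost is a short change to the SAP text, about 19–20 model degrees of freedom per parameter, and longer tables. Two parameters with 21 times and nine with 20 give 2 × 21 + 9 × 20 = 222 time-specific comparisons, of which about 222 × 0.05 = 11 would be nominally significant by chance if there were no effects. Hence the descriptive label.

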- Partial thromboplastin time (PTT), prothrombin time [(PT); PT/INR], hemoglobin/hematocrit and platelet count will be measured at baseline, initiation and at least once daily (post-randomization) up to 120 hours of study CRRT (see Appendix 1).
- Liver function tests are to be measured at baseline, initiation and then as determined by local standard-of-care (see Appendix 1).

During the Treatment Period, if a Prismaflex M150 Set clots or reaches an unacceptable circuit pressure as indicated by machine alarms/conditions, it will be replaced. The Prismaflex M150 Set will also be replaced after 72 hours of continuous use (ie, "Advisory Time to Change Set") or any time the patient (prior to 72 hours of use) must temporarily stop CRRT (eg, CT scan, etc.). In these cases, the filter set will be replaced before continuing CRRT.

Treatments will be performed according to this clinical protocol and in conjunction with the Operator's Manual for the Prismaflex System (Version 7.xx Software) and the Instructions for Use (IFU) for the Prismaflex M150 Set, respectively. Study sites, especially those who do not currently use the Prismaflex M150 Set, should carefully review the Prismaflex M150 Set IFU "Warnings" section #3 and "Hypersensitivity

Reactions" section as special attention must be paid to patients receiving ACE inhibitors and/or having already shown similar hypersensitivity reactions. The Principal Investigator (PI) or a trained healthcare professional must be present at all times during CRRT to immediately address and manage any clinical concerns or other issues. All recommendations and warnings mentioned in the Operator's Manual and IFU shall be strictly followed.

Recommendations for the initial flow rates in the experimental arm of Prismocitrate 18, post-dilution replacement solution, and dialysate are provided to the investigator (refer to Section 5.2.2.2). However, according to the clinical manifestations and needs of the patient, the local standard-of-care for CRRT may be instituted based upon the investigator's medical judgement. For the control arm, investigators are advised to use standard-of-care practices per their local institution. However, all such prescription data must be recorded on the eCRFs and adhere to the following general guidelines in both arms of the trial:

- Modality must be CVVHDF
- Minimum prescribed CVVHDF dose (based on total effluent volume) - 25 mL/kg/hour.
- Minimum BFR 100 mL/minute.

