5.2.2 Study Arm Protocols

Participating investigator sites will use the following general guidelines for CRRT:

- Modality must be CVVHDF
- Minimum prescribed CVVHDF dose (based on total effluent volume) - 25 mL/kg/hour.
- Minimum BFR 100 mL/minute.
- Experimental Arm Maximum BFR 200 mL/minute.
- Control Arm Maximum BFR 400 mL/minute. This maximum BFR allows centers to follow their local standard-of-care procedures related to higher BFR use in non-anticoagulated circuits
- Minimum post-filter replacement fluid rate of 200 mL/hour for de-aeration chamber
- Minimum pre-blood pump infusion of 1000 mL/hour (either citrate or replacement fluid depending on the study arm)

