7.4.2 Treatment Prescription – initial and all changes during Treatment Period

1. Patient fluid removal flow rate (mL/hour).

- 2. Post-filter replacement flow rate (mL/hour).
- 3. Blood flow rate (mL/minute).
- 4. Dialysate flow rate (mL/hour).
- 5. Prismocitrate 18 flow rate (mL/hour).
- 6. Calcium Gluconate or calcium chloride infusion details: dilution and rate (mL/hour).

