alarms/conditions occur after which the study CRRT treatment will be terminated and the patient will end the treatment period if mitigation of the following alarms is not possible: "Warning: Filter Clotted" and/or "Advisory TMP Too High".

- ^f Blood access information will include catheter-type, manufacturer, length & size, and catheter anatomical insertion location.
- g CRRT treatment modality will be confirmed as CVVHDF (Hemodiafiltration).
- ^h CRRT prescription will include patient fluid removal flow rate (mL/hour), post-filter replacement flow rate (mL/hour), PBP flow rate (mL/hour), BFR (mL/hour), dialysate flow rate (mL/hour), Prismocitrate 18 flow rate (mL/hour) and calcium gluconate or calcium chloride infusion details.
- ¹ Priming solution formulation, brand name/manufacturer; Dialysate and replacement solution prescription information will include the brand name/manufacturer, formulation, and volume. The initial prescription will be recorded along with any changes throughout the Treatment Period.
- Anticoagulation information will include confirmation if the patient was randomized to 'Prismocitrate 18' or 'no systemic anticoagulation'.
- ^k Clinical laboratory evaluations are presented in detail in Appendix 1.
- ¹ Blood pressure including mean arterial pressure is collected at baseline (after randomization but before the initiation of study CRRT) and at 6 hour intervals during the Treatment Period up to 120 hours of study CRRT, as well as at End of Treatment.
- ^mEffluent volume (in mL) will be recorded from the Prismaflex System history screen. In the Prismaflex software, the starting time for the charting interval will be set (eg, at 8:00 am) and the volumes and doses will be stored for each day starting at that time.
- ⁿ Bleeding events information will include number, location, duration, estimated blood loss, and adverse event data (if applicable).
- ^o All blood transfusions information will include: (number, type, and number of units infused), relevant laboratory parameters (ie, hemoglobin/hematocrit and platelet values, etc.), as well as adverse event data (if applicable).
- ^p Patient Fluid Removal data collection will include post-treatment weight, the amount of fluid removed, and administration of input therapeutic fluids.

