6.2.2 Per-Protocol Analysis Set (PP)

The Per-Protocol Analysis Set (PP) defines a subset of the FA including patients who

- fulfill all inclusion criteria
- do not meet any of the exclusion criteria
- were randomized and treated according to the randomization scheme
- received at least 80% of their prescribed CRRT dose
- do not have major protocol deviations that might impact the assessment of the primary endpoint (e.g., mechanical malfunction of the machine)
- have available survival data for extracorporeal circuit life of at least one circuit
 (i.e., time to occurrence of Prismaflex System alarms/conditions as outlined in
 Section 5.5.1 Primary Efficacy Endpoint, or censored circuit life if no system
 alarms/conditions occurred until the circuit was used for 72 continuous hours or if
 CRRT was stopped during the evaluation period for reasons other than system
 alarms/conditions).

The Per Protocol Set will be analyzed based upon the subjects randomized treatment.

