If one of the rate is missing, effluent rate will not be able to calculate.

The prescribed dose (effluent rate) is calculated as:

Prescribed Effluent Rate = Body Weight \times 25 mL/kg/hr

If there are multiple records of effluent rate per day (e.g. due to infusion rate change) the average value will be used to calculate the delivered dose for that day.

The percentage of the prescribed dose actually administered to the patient will be calculated by dividing the actual effluent rate by the prescribed effluent rate. Differences between treatment groups in the percentage of overall prescribed dose actually administered will be assessed on a 5% significance level using a two-sided t-test or Wilcoxon rank sum test, as applicable. However, the statistical test will only be carried out conditional upon a significant test result for the primary endpoint at the time point of the interim analysis or final analysis. This hierarchical test procedure guarantees that the overall Type I error is controlled and preserved at a maximum of 5%.

The analysis of secondary efficacy endpoints will be carried out on the FA based on the randomized treatment groups (intent-to-treat principle).

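### Followed as written, the SAP 13.3 effluent formula leaves out Control's pre-blood pump fluid, which biases or disables the gated dose test and conflicts with SAP 5.5.2

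*SAP*

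**What the plan says.** **The formula.** SAP 13.3 states that "prescribed and delivered CRRT dose will be derived as follows based on the University of Alabama at Birmingham Continuous Venovenous Hemodiafiltration Protocol". It then sets Q_E = Q_PBP + Q_D + Q_FR + Q_R for all patients. Q_PBP is the "pre-blood pump infusion rate which is the Prismocitrate 18 flow rate (mL/hour", with no limit to one arm and no Control alternative. Q_R covers post-filter replacement fluid only. The section adds: "If one of the rate is missing, effluent rate will not be able to calculate". Percentage of dose is the actual effluent rate divided by body weight × 25 mL/kg/h.

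**The Control circuit.** Protocol 5.2 says prescriptions must "adhere to the following general guidelines in both arms of the trial". One of these guidelines, repeated in 5.2.2, is: "Minimum pre-blood pump infusion of 1000 mL/hour (either citrate or replacement fluid depending on the study arm".

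**The other derivation.** SAP 5.5.2 and Protocol 5.2 and 6.7.2 base delivered dose on daily recorded effluent volume and patient weight. Protocol 5.2 takes that volume from the machine's history screen.

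**Data items.** Protocol 7.4.2 lists "Prismocitrate 18 flow rate (mL/hour" but no pre-blood pump flow. Footnote h of Protocol Appendix 2, repeated under SAP Table 1, lists "post-filter replacement flow rate (mL/hour), PBP flow rate (mL/hour" as well as the Prismocitrate flow.

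**Where the percentage is used.** SAP 13.3 tests the percentage between arms at 5%, only if the primary endpoint is significant. SAP 6.2.2 limits the Per-Protocol Set to patients who "received at least 80% of their prescribed CRRT dose".

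**The concern.** The Q_PBP definition fits the Prismocitrate arm, where the pre-blood pump delivers Prismocitrate 18. The matching Protocol wording is in 5.2.2.2.1, under a parent section whose initial prescription is only for that arm. Applied to Control, it points to a flow that does not exist, and the replacement fluid actually passing through the pre-blood pump falls outside all four terms.

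The error affects one arm only, so it does not cancel in a between-arm comparison. The comparison concerned is the only secondary test gated on the primary result. The SAP document history says that wording was added because such endpoints might support further labelling claims. If the Per-Protocol cut uses the same percentage, the robustness check on the primary endpoint would also lose Control patients selectively.

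**Working it through.** **Inputs from the documents:** dose denominator 25 mL/kg/h × weight W (SAP 13.3); Control pre-blood pump flow of at least 1000 mL/h (Protocol 5.2, 5.2.2); 80 patients per arm, with an interim look when 50% have completed (SAP 5.2, 13.5); Per-Protocol cut of 80% (SAP 6.2.2).

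**Assumptions, not in the documents:** whether Control's Prismocitrate flow is stored as blank or zero; the true dose and weight distributions; and the SD of the percentage, taken as 10 to 50 points.

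**1. The plan's own figure.** Protocol 5.2.2.2.1 gives 2,250 mL/h for a 90 kg patient: 90 × 25 = 2,250. Reproduced.

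**2. Blank case.** A component of Q_E is missing, so the SAP's missing-rate rule makes every Control effluent rate not calculable. There is no Control percentage to compare.

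**3. Zero case.** For a true dose of d mL/kg/h and pre-blood pump flow at its 1000 mL/h minimum:

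- Computed percentage = (d × W − 1000) / (25 × W).
- Correct percentage = d / 25.
- Shortfall = 1000 / (25 × W) = 40 / W, whatever the true dose.

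At 90 kg and d = 25, this is (2,250 − 1,000) / 2,250 = 1,250 / 2,250 = 55.6% instead of 100%. A pre-blood pump flow above 1000 mL/h lowers the score further.

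| Weight (kg) | Shortfall (points) | Score at d = 25 (true 100%) | Score at d = 30 (true 120%) | Score at d = 35 (true 140%) |
|---|---|---|---|---|
| 70 | 57.1 | 42.9% | 62.9% | 82.9% |
| 90 | 44.4 | 55.6% | 75.6% | 95.6% |
| 120 | 33.3 | 66.7% | 86.7% | 106.7% |
| 150 | 26.7 | 73.3% | 93.3% | 113.3% |
| 200 | 20.0 | 80.0% | 100.0% | 120.0% |

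**4. Effect on the gated test in the zero case.** Suppose the arms truly do not differ and Control is shifted down by Δ points. The probability of a significant result favouring Prismocitrate is about Φ(Δ / (SD × √(2/n)) − 1.96).

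- n = 80, Δ = 44.4, SD = 50: 44.4 / 7.906 = 5.62, giving 99.99%. At SD 10 to 40 it rounds to 100%.
- n = 80, Δ = 26.7, SD = 50: 26.7 / 7.906 = 3.38, giving 92%.
- If the trial stops at the interim look, with about 40 per arm, SD = 50 gives 98% for Δ = 44.4 and 67% for Δ = 26.7.

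These use a single Δ. In the trial the shift would be the mean of 40 / W over Control weights, or larger where flow exceeds 1000 mL/h.

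**5. Effect on the 80% cut, if it uses this percentage.** In the zero case, (d × W − 1000) / (25 × W) ≥ 0.80 requires W ≥ 1000 / (d − 20). That is 200 kg at d = 25, 100 kg at d = 30 and 66.7 kg at d = 35.

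**The case against.** The strongest reply is that the documents already contain what a correct calculation needs:

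- SAP 5.5.2 and the Protocol define delivered dose from recorded effluent volume, which includes whatever Control receives before the blood pump. On that derivation the artefact is zero.
- Footnote h collects pre-blood pump flow separately from Prismocitrate flow and for both arms. The SAP also plans a listing of the pre-blood pump solutions used (16.2.9.14). A programmer could read the Prismocitrate clause as a gloss and use the collected field.
- The Per-Protocol criterion does not cite 13.3.
- Protocol 7.4.2 is a collection list, not a formula, and 7.4.11 separately records total fluid input and output, including effluent.
- Protocol 5.2.2.2.1 sits under a Prismocitrate-arm heading, but one of its bullets sets dose targets for both groups.

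Most of this stands. A reader might infer that no valid dose calculation exists for Control, or that its data would be lost. The documents do not support either inference.

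The reply does not rescue 13.3 itself. That section is the analysis instruction, its formula does not refer to the separate pre-blood pump field, and its rule for averaging several effluent-rate records in a day shows that delivered dose is meant to come from flow rates. The both-groups bullet gives Control no Q_PBP definition. SAP 12 declares no departure from the protocol, so nothing says which derivation prevails. A gated test in an open-label trial should not depend on an unwritten correction.

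**Conclusion.** The Q_PBP definition in SAP 13.3 is wrong for Control as written, and it conflicts with the recorded-volume derivation in SAP 5.5.2. Programmed literally, it leaves Control with no dose percentage, or lowers each Control percentage by at least 40 / W of the 25 mL/kg/h reference (44.4 points at 90 kg). The first outcome disables the gated test. The second would very probably produce a false result in favour of Prismocitrate across most of the assumed SD range. Both depend on 13.3 prevailing over 5.5.2 and on how the Control field is stored, neither of which is stated.

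Two stronger readings are tempting:

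- **That nearly all Control patients would drop out of the Per-Protocol Set.** This is conditional. SAP 13.3 holds the SAP's only definition of the percentage, but 6.2.2 does not refer to it. Even in the zero case, exclusion of most Control patients follows only near 25 mL/kg/h, which the Protocol sets as a minimum. At 30 or 35 mL/kg/h many would pass, depending on weight. The dose distribution is not given.
- **That the primary result is compromised.** It is not. The circuit-life analysis on the Full Analysis Set does not use the effluent rate. The gated secondary test, the dose and exposure summaries and, conditionally, the Per-Protocol sensitivity analysis are what is at risk.

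**What to change.** 1. In SAP 13.3, define Q_PBP as the total pre-blood pump flow of whichever solution the arm uses, taken from the pre-blood pump flow field in footnote h and counted once.
2. Reconcile 13.3 with the recorded-effluent-volume derivation in 5.5.2, and state which one drives the gated test.
3. In SAP 6.2.2, state which derivation drives the 80% criterion.
4. Add the pre-blood pump flow to the Protocol 7.4.2 list so that it matches Appendix 2 footnote h and Control's flow is recorded.

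The cost is a few SAP sentences and one line in the Protocol. The field is already listed in Appendix 2, and no change to the sample size or the primary analysis is needed. Correcting Q_PBP alone would leave the conflict with 5.5.2 open.
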